## **14 DATA HANDLING AND ADMINISTRATIVE REQUIREMENTS**

### **14.1 Subject Confidentiality**

The Investigator must ensure that the subject's anonymity is maintained throughout the course of the study. In particular, the Investigator must keep an enrollment log with confidential identifying information that corresponds to the subject numbers and initials of each study participant. At the end of the clinical study, the Study Sponsor will collect a copy of the enrollment log **without any identifying subject information**. All documents submitted to the Study Sponsor will identify the subjects exclusively by number and demographic information. No other personally identifying information will be transmitted to the Study Sponsor.

The Study Sponsor may release anonymized study data to external researchers for purposes of future research directly related to the study objectives, or future research that is beyond the scope of the current study objectives. The ICF explains this to study subjects. Anonymization means that all identifiable information will be removed from the dataset and all links to the subjects in the study will be removed. Anonymization of the data will maintain confidentiality of the subjects who participate in the study so that they cannot be identified by external researchers. The anonymized data set will contain records from all of the subjects in the current study, but the anonymization process might change the data set in some ways, so external researchers will be informed that they might not be able to duplicate some of the results from this study.

External researchers who request permission to use anonymized data from studies for a new medicine or new indication of a medicine (studies for approved medicinal products, small molecule generics, and devices are excluded) must be approved by a central independent review panel that will adjudicate the scientific request and the competency of the external researcher(s), as well as the determine applicability to current standard operating procedures (SOPs). If approved, a data sharing agreement will be executed between the Study Sponsor and the external researcher(s), committing to a specified analysis and publication timeline.

Anonymized data will be released to external researchers only after EU and/or US submission of the investigational drug/biologic for the study indication. The Study Sponsor will not be able to influence the analyses that are performed by external researchers using the data from this study once the anonymized data are released.

## **14.2 Completion of Source Documents and Case Report Forms**

The nature and location of all source documents will be identified to ensure that original data required to complete the eCRFs exist and are accessible for verification by the site monitor, and all discrepancies must be appropriately documented via the query resolution process. Study monitors are appointed by the Study Sponsor and are independent of study site staff.

If electronic records are maintained, the method of verification must be determined in advance of starting the study.

At a minimum, source documents include the following information for each subject:

- Subject identification (name, sex, race/ethnicity)
- Documentation of subject eligibility
- Date of informed consent
- Dates of visits
- Documentation that protocol specific procedures were performed
- Results of study parameters, as required by the protocol
- IP accountability records
- Documentation of AEs and other safety parameters (if applicable)
- Records regarding medical histories and the use of concomitant therapies prior to and during the study
- Date of study completion and reason for early discontinuation, if applicable

It is required that the author of an entry in the source documents be identifiable. Direct access to source documentation (medical records) must be allowed for the purpose of verifying that the data recorded on the eCRF are consistent with the original source data.

Only designated individuals at the site will complete the eCRFs. The eCRFs must be completed at regular intervals following the clinical study visit schedule. It is expected that all data reported have corresponding entries in the source documents. The Principal Investigator is responsible for reviewing and certifying that the eCRFs are accurate and complete. The only subject identifiers recorded on the eCRFs will be subject number, and subject demographic information.

### **14.3 Data Review and Clarifications**

A targeted review of eCRF data to the subject's source data will be completed by the site monitor to ensure completeness and accuracy. After the eCRFs have been completed, additional data clarifications and/or additions may be needed as a result of the data cleaning process. Data clarifications are documented and are part of each subject's eCRF.

### **14.4 Sponsor and Monitoring Responsibilities**

The Study Sponsor will designate a monitor to conduct the appropriate site visits at the appropriate intervals. The clinical investigation will be monitored to ensure that the rights and well-being of the subjects are protected, the reported data are accurate, complete, and verifiable from the source documents, and the study is conducted in compliance with the current approved protocol (and amendments[s], if applicable), with current GCP, and with applicable regulatory requirements.

All sites must have a site initiation. Prior to screening subjects or performing the informed consent process on any subject, the site must receive a Site Activation Notification from an appropriate Study Sponsor representative. Monitoring will be conducted periodically while the clinical study is ongoing. Monitoring methods may include site visits, telephone, written and fax correspondence. Close-out visits will take place after the last visit of the last subject or after database lock.

A Coordinating Investigator (CI) may be identified by the Study Sponsor. In cases where a CI is required, the Study Sponsor will select the CI based upon their experience, qualifications, active study participation, and their willingness and availability to take on this role. The CI will be bound by confidentiality obligations described in a separate confidentiality agreement between the CI and the Study Sponsor.

Additionally, a Study Sponsor representative will provide training on proper operation of the Topcon KR-1W Wavefront Analyzer and other study assessments as appropriate. Detailed instructions are covered in the MOP. A copy of collected images from study assessments may be sent electronically to the Sponsor. These images must be masked to subject identification information.

### **14.5 Regulatory Documentation and Records Retention**

The Investigator is required to maintain up-to-date, complete regulatory documentation as indicated by the Study Sponsor and the Investigator's files will be reviewed as part of the

ongoing study monitoring. Financial information is not subject to regulatory inspection and is to be kept separately.

Additionally, the Investigator must keep study records and source documents until the Study Sponsor provides written approval for their destruction. If the Investigator retires, relocates, or for any other reason withdraws from responsibility of keeping the study records, then the Study Sponsor must be notified and suitable arrangements made for retention of study records and source documents needed to comply with national and international regulations (generally 2 years after discontinuing clinical development or after the last marketing approval).

## **14.6 Quality Assurance and Quality Control**

The Study Sponsor will secure agreement from all involved parties to ensure direct access to all study related sites, source data and documents, and reports for the purpose of monitoring and auditing by the Study Sponsor, and inspection by domestic and foreign regulatory authorities. Quality control will be applied to each stage of data handling to ensure that all data are reliable and have been processed correctly. Agreements made by the Study Sponsor with the Investigator/Institution and any other parties involved in the clinical study will be provided in writing as part of the protocol or as a separate agreement.

## **15 ETHICS**

This clinical study must be conducted in accordance with the ethical principles contained within:

- The Declaration of Helsinki (DoH), and in compliance with the International Conference on Harmonization (ICH) E6 GCP Consolidated Guideline
- ISO 14155:2011 Clinical investigation of medical devices for human subjects – Good clinical practice
- SOPs of the Study Sponsor and contract research organizations participating in the conduct of the clinical study and all other applicable regulations.

The Investigator and all clinical study staff must conduct the clinical study in compliance with the protocol. The Investigator must ensure that all personnel involved in the conduct of the study are qualified to perform their assigned responsibilities through relevant education, training, and experience.

Before clinical study initiation, this protocol, the ICF, any other written information given to subjects, and any advertisements planned for subject recruitment must be approved by an

IEC/IRB. The Investigator must provide documentation of the IEC/IRB approval to the Study Sponsor. The approval must be dated and must identify the applicable protocol, amendments (if any), ICF, all applicable recruiting materials, written information for subject, and subject compensation programs. The IEC/IRB must be provided with a copy of the any periodic safety updates, and all other information as required by local regulation and/or the IEC/IRB. At the end of the study, the Investigator must notify the IEC/IRB about the study's completion. The IEC/IRB also must be notified if the study is terminated prematurely. Finally, the Investigator must report to the IEC/IRB on the progress of the study at intervals stipulated by the IEC/IRB.

Voluntary informed consent must be obtained from every subject prior to the initiation of any screening or other study-related procedures. The Investigator must have a defined process for obtaining consent. Specifically, the Investigator, or delegate, must explain the clinical study to each potential subject and the subject must indicate voluntary consent by signing and dating the approved ICF. The subject must be provided an opportunity to ask questions of the Investigator, and if required by local regulation, other qualified personnel. The Investigator must provide the subject with a copy of the consent form written in a language the subject understands. The consent document must meet all applicable local laws and provide subjects with information regarding the purpose, procedures, requirements, and restrictions of the study, along with any known risks and potential benefits associated with the IP, the available compensation, and the established provisions for maintaining confidentiality of personal, protected health information. Subjects will be told about the voluntary nature of participation in the study and must be provided with contact information for the appropriate individuals should questions or concerns arise during the study. The subject also must be told that their records may be accessed by appropriate authorities and Sponsor-designated personnel. The Investigator must keep the original, signed copy of the consent and must provide a duplicate copy to each subject according to local regulations.

The Study Sponsor assures that the key design elements of this protocol will be registered in [www.clinicaltrials.gov](http://www.clinicaltrials.gov) as required by current regulations and, if applicable, other public databases as required by local country regulations. In addition, results of this study will be made publicly available in [www.clinicaltrials.gov](http://www.clinicaltrials.gov) regardless of outcome as required by current regulations and, if applicable, in other public databases as required by local country regulations.

Amendments may necessitate that the informed consent and other study-related material be revised. If the consent form is revised, all subjects currently enrolled in the study must sign the approved, revised informed consent, as required by the IEC/IRB.

Alcon - Business Use Only

Document: TDOC-0052874

Status: Effective

Effective Date: 01-Sep-2016

Version: 2.0; CURRENT; Most-Recent; Effective

Short Title:

Statistical Analysis Plan

ILQ732-I001 /

NCT02842151

Full Title:

Statistical Analysis Plan

ILQ732-I001

Protocol Title: Optimizing the Assessment of Refractive Outcomes after
Cataract Surgery and Implantation of a Monofocal IOL

Project Number: A01983

Protocol TDOC Number: TDOC- 0050597

Author:

[REDACTED]

[REDACTED]

Approvals: See last page for electronic approvals.

Job Notes:

This is the original (Version 1.0) Statistical Analysis Plan for this study. This version of the Statistical Analysis Plan is based on Version 1.0 of the study protocol.

Printed By:

Print Date:

Alcon - Business Use Only**Effective Date:** 01-Sep-2016**Document:** TDOC-0052874**Version:** 2.0; CURRENT; Most-Recent; Effective**Status:** Effective**Executive Summary:****Key Objectives:**

To demonstrate equivalency, at each of the 3 clinical sites, between IOL SRK/T A-constant (Retzlaff et al., 1990) estimated based on postoperative manifest spherical equivalent refraction at 3 months and IOL A-constant estimated based on postoperative spherical equivalent from autorefraction using *Topcon® KR-1W* at 3 months.

Decision Criteria for Study Success:

The study will be considered a success if, the primary objective is met.

A two-sided 90% confidence interval will be constructed for the mean of the paired difference between the two estimated SRK/T A-constants separately for each site. If all the two-sided 90% confidence intervals fall within (-0.15, 0.15), then equivalence will be concluded.

Alcon - Business Use Only

Effective Date: 01-Sep-2016

Document: TDOC-0052874

Version: 2.0; CURRENT; Most-Recent; Effective

Status: Effective

5.3.3	Surgical Problems	14
5.3.4	Intraocular Pressure.....	14
5.3.5	Slit Lamp Examination	14
5.3.6	IOL Observations	14
5.3.7	IOL Position Change.....	14
5.3.8	Subjective Posterior Capsule Opacification.....	15
5.3.9	Posterior Capsulotomy.....	15
5.3.10	Dilated Fundus Examination.....	15
5.4	Interim Analysis for Safety	15
6	Analysis Strategy for Other Endpoints.....	15
7	Sample Size and Power Calculations	15
8	References	16
9	Deviations from Protocol	16
10	Revision History.....	16

List of Tables

Table 1-1	Schedule of Study Visits	6
-----------	--------------------------------	---

List of Figures

[figure not shown]
Figure 4-1	Cumulative Line Plot	11
------------	----------------------------	----

1 Study Objectives and Design

1.1 Study Objectives

The primary objective of this study is to demonstrate equivalency at each of the 3 clinical sites, between IOL SRK/T A-constant estimated based on postoperative manifest spherical equivalent refraction at 3 months and IOL SRK/T A-constant estimated based on postoperative spherical equivalent from autorefraction using *Topcon KR-1W* at 3 months. The primary endpoints to be used for the primary analysis are:

- IOL SRK/T A-constant estimated based on the preoperative biometry, IOL power and postoperative manifest spherical equivalent refraction at 3 months and
- IOL SRK/T A-constant estimated based on the preoperative biometry, IOL power and postoperative spherical equivalent from autorefraction using *Topcon KR-1W* at 3 months.

1.2 Study Description

This is a prospective, non-randomized, observer-masked (*examiner performing manifest refraction is masked to the refractive target and refractive error from the surgical planning and the operative visit*), interventional clinical study. The Investigator will determine the study eye to be included in this study. Only the study eye will be followed throughout the study. At a minimum 165 subjects will be enrolled at up to 3 sites in the United States and Ireland.

Subjects require cataract surgery with implantation of a monofocal IOL Model SN60WF in the capsular bag in one or both eyes to qualify for enrollment into this study. One eye will be enrolled per subject.

A total of 4 scheduled visits are planned including the Screening/Visit 0 and the Operative Visit/Visit 00. Scheduled postoperative visits must occur at the following intervals: 20-40 days and 80-100 days. See Table 1-1 Schedule of Study Visits.

Table 1-1 Schedule of Study Visits

Time from Implantation	Study Visit
Screening / Preoperative (Day -28 to Day 0)	Visit 0
Operative (Day 0)	Visit 00
20-40 days	Visit 1
80-100 days	Visit 2

1.3 Randomization

This is a non-randomized study. All subjects will be implanted with Model SN60WF IOL in the selected study eye.

1.4 Masking

The examiner performing the manifest refraction will be masked to the refractive target and refractive error from the surgical planning and the operative visit, respectively. There is no other masking.

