## 5 SCHEDULE OF PROCEDURES AND ASSESSMENTS

Visit	Visit 0 	Visit 00	Visit 1	Visit 2	Early Exit
Visit Type	Screening	Operative	Post-Op	Post-Op	
Day Number	Day -28-0	Day 0	Day 20-40	Day 80-100	N/A
Informed Consent	X				
Demographics	X				
Medical History	X	X	X	X	X
Concomitant Medications	X	X	X	X	X
Inclusion/Exclusion	X	X			
Urine Pregnancy Test 	X				
Anterior Chamber Depth	X			X	
Axial Length	X			X	
White-to-White Distance	X			X	
Lens Thickness	X		X	X	
Manifest Refraction	X		X	X	X
Keratometry	X			X	
Autorefracton ( Topcon KR-1W )	X		X	X	
Uncorrected Distance VA (4 m)	X		X	X	X
Corrected Distance VA (4 m)	X		X	X	X
Pupil Diameter (dilated / undilated)	X	X		X	
Target Residual Refractive Error	X				
IOL Power Calculation	X				
Slit-Lamp Examination	X		X	X	X
Dilated Fundus Examination	X			X	X
Intraocular Pressure	X		X	X	X
Actual Lens Position				X	
Capsulorhexis Diameter				X	
Operative Eye		X			
Lens Information		X			
Folding and Insertion Instrument		X			
Final Incision Size		X			
Incision Location		X			
Problems during Surgery		X			
Other Surgical Procedures		X			
Subjective PCO			X	X	X
Posterior Capsulotomy			X	X	X
IOL Observations			X	X	X
IOL Position Change			X	X	X
Adverse Events	X	X	X	X	X
Secondary Surgical Interventions		X	X	X	X
Device Deficiencies		X	X	X	X

 Operative Visit (Visit 00) must occur within 28 calendar days from Screening/Visit (Visit 0)

 Women of child-bearing potential only

Printed By:

Print Date:

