#### **10.4 Treatment Masking**

The examiner performing the manifest refraction must be masked to the refractive target and refractive error from the surgical planning and the operative visit, respectively.

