### **11 STUDY PROCEDURES AND ASSESSMENTS BY VISIT**

The following section outlines the assessments to be performed in this clinical study. Assessments are described in detail in the ILQ732-I001 MOP, and are outlined in tabular format in Section 5 of this protocol.

AEs, SAEs including SSIs and device deficiencies are assessed and reported at all scheduled and unscheduled visits (UNSV) for each subject, beginning at the time the informed consent is obtained.

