### **11.3 Postoperative Visit (Visit 1)**

#### **Visit 1: 20-40 Days Post Study Eye Implantation**

Below is a list of procedures to be completed at Visit 2. All assessments must be documented in source documentation and eCRF, if applicable.

**NOTE:** All postoperative assessments to be completed monocularly on the operative eye only, as applicable.

1. Document any changes to medical/ocular history and ocular and non-ocular concomitant medications.
2. Record lens thickness of the IOL.
3. Capture aberrometry, topography, keratometry, pupillometry and autorefractometry with the Topcon KR-1W Wave-Front Analyzer.
4. Perform manifest refraction.
5. Measure and record UDVA and CDVA.
6. Perform slit-lamp examination of the anterior segment. Include documentation of IOL observations, if any.

7. Observe any IOL position changes (ie, tilt and decentration) occurring since the previous visit.
8. Assess subjective PCO, and record information for any PC that has occurred since surgery, if applicable.
9. Perform tonometry to measure IOP.
10. Record any AEs including SSIs

**NOTE:** SAEs including SSIs must be entered into the eCRF within 24 hours of the Investigator's knowledge. Refer to Section 12 for further details.

11. Record any device deficiencies. Refer to Section 12 for further details.

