## **11.4 Postoperative Visit (Visit 2)**

### **Visit 2: 80-100 Days Post Study Eye Implantation**

Below is a list of procedures to be completed at Visit 3. All assessments must be documented in source documentation and eCRF, if applicable.

**NOTE:** All postoperative assessments to be completed monocularly on the operative eye only, as applicable.

1. Document any changes to medical/ocular history and ocular and non-ocular concomitant medications.
2. Assess ACD, AL and white-to-white distance.
3. Assess lens thickness of the IOL.
4. Perform keratometry measurements to evaluate the curvature of the anterior surface of the eye.
5. Capture aberrometry, topography, keratometry, pupillometry and autorefraction with the Topcon KR-1W Wave-Front Analyzer.
6. Record actual lens position, the plane bisecting the IOL.
7. Record capsulorhexis diameter.
8. Perform manifest refraction.

9. Measure and record UDVA and CDVA.
10. Measure and record photopic pupil diameter (dilated and undilated).
9. Perform slit-lamp examination of the anterior segment. Include documentation of IOL observations, if any.
10. Conduct dilated fundus examination.
11. Observe any IOL position changes (ie, tilt and decentration) occurring since the previous visit.
12. Assess subjective PCO, and record information for any PC that has occurred since surgery, if applicable.
13. Perform tonometry to measure IOP.
14. Record any AEs including SSIs

**NOTE:** SAEs including SSIs must be entered into eCRF within 24 hours of the Investigator's knowledge. Refer to Section 12 for further details.

15. Record any device deficiencies. Refer to Section 12 for further details.

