## 12.8 Unmasking of the Study Information

This study is not masked. However the examiner performing manifest refraction is masked to the refractive target and refractive error from the surgical planning and the operative visit.

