4.1 Efficacy Endpoints

The primary [REDACTED] endpoints are:

- IOL SRK/T A-constant estimated based on the preoperative biometry, IOL power and postoperative manifest spherical equivalent refraction at 3 months and
- IOL SRK/T A-constant estimated based on the preoperative biometry, IOL power and postoperative spherical equivalent from autorefractometry using *Topcon KR-1W* at 3 months.

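### The examiner doing manifest refraction is not masked to the KR-1W reading and the order of the two tests is not set, so any anchoring on the device would favour equivalence

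*SAP*

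**What the plan says.** SAP 1.4 sets out the mask on the manifest-refraction examiner as follows: "masked to the refractive target and refractive error from the surgical planning and the operative visit, respectively. There is no other masking". Protocol 10.4 has the same scope: "The examiner performing the manifest refraction must be masked to the refractive target and refractive error from the surgical planning and the operative visit, respectively". Protocol 12.8 says: "This study is not masked. However the examiner performing manifest refraction is masked to the refractive target and refractive error from the surgical planning". Protocol 8.1 and 8.2 repeat this limited mask. None of these sections mentions the KR-1W result.

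The first primary endpoint in SAP 4.1 is the "IOL SRK/T A-constant estimated based on the preoperative biometry, IOL power and postoperative manifest spherical equivalent refraction at 3 months". The second is built in the same way from the KR-1W spherical equivalent. SAP 4.3 analyses the paired difference at each site.

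On order, the numbered lists put the device first. At Visit 2 (Protocol 11.4), item 5 is "Capture aberrometry, topography, keratometry, pupillometry and autorefraction with the Topcon KR-1W Wave-Front Analyzer" and manifest refraction is item 8. At Visit 1 (Protocol 11.3), KR-1W capture is item 3 and "Perform manifest refraction" is item 4. At Visit 0 (Protocol 11.1), they are items 7 and 8. The Protocol Section 5 table has the "Manifest Refraction" row above the autorefraction row. No text makes either listing a required sequence. Protocol 11 adds: "Assessments are described in detail in the ILQ732-I001 MOP, and are outlined in tabular format in Section 5 of this protocol".

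**The concern.** Biometry and lens power are common to both A-constants, so they cannot separate the two values within an eye. Only the refractions can. Manifest refraction is the subjective one, and its examiner may know the comparator's answer. The existing mask covers surgical planning and the operative visit. It does not reach a device reading taken at a follow-up visit, and the schedule has no KR-1W capture at the operative visit.

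If the examiner starts from the device reading or drifts toward it, the two measurements stop being independent. The paired difference then moves toward zero and may also vary less. In a superiority trial that would usually work against the sponsor. Here the claim is that the 90% interval lies inside ±0.15, so both effects help the claim. The question whether autorefraction can stand in for manifest refraction in A-constant personalization needs two readings made without knowledge of each other.

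**Working it through.** **Inputs from the documents.** Margin ±0.15 and a two-sided 90% paired t interval per site (SAP 4.3); 48 evaluable subjects per site and SD of the paired difference 0.35 (SAP 7); equivalence required at every site (SAP 4.4).

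**Assumptions not in the documents.** The pull w of manifest refraction toward the KR-1W value, taken as 0, 0.1, 0.2 and 0.3; independent sites; and an A-constant that is close to linear in refraction over small differences.

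**Step 1: the plan's own figure.** SE = 0.35/√48 = 0.0505; t(0.95, 47 df) = 1.678; half-width = 1.678 × 0.0505 = 0.085. The exact probability that the interval lies inside ±0.15 at true difference 0, integrated over the sample SD, is 80.0% per site. The stated 90% is reproduced only as the power of a single one-sided paired t-test (89.99%). That is a separate matter, and nothing below depends on the 90%.

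**Step 2: effect of a pull.** If the recorded manifest value is MR + w(AR − MR), the observed difference is (1 − w)(MR − AR). A true mean of 0.15 becomes 0.15(1 − w). In case A the SD shrinks by the same factor; in case B the SD stays at 0.35.

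**Step 3: probability of declaring equivalence at one site.**

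| w | Observed mean | SD, case A | True 0.15, case A | True 0.15, case B | True 0, case A | True 0, case B |
|---|---|---|---|---|---|---|
| 0 | 0.150 | 0.350 | 5.0% | 5.0% | 80.0% | 80.0% |
| 0.1 | 0.135 | 0.315 | 9.3% | 8.8% | 89.2% | 80.0% |
| 0.2 | 0.120 | 0.280 | 18.1% | 14.5% | 95.6% | 80.0% |
| 0.3 | 0.105 | 0.245 | 34.8% | 22.1% | 98.9% | 80.0% |

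**Step 4: study level under the every-site rule.** With all three sites at 0.15, the probability is the cube of the per-site value. With one site at 0.15 and two at 0, it is the per-site value at 0.15 times the square of the value at 0.

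| w | All three at 0.15, A | All three at 0.15, B | One at 0.15, two at 0, A | One at 0.15, two at 0, B |
|---|---|---|---|---|
| 0 | 0.01% | 0.01% | 3.2% | 3.2% |
| 0.1 | 0.08% | 0.07% | 7.4% | 5.6% |
| 0.2 | 0.6% | 0.3% | 16.5% | 9.2% |
| 0.3 | 4.2% | 1.1% | 34.0% | 14.1% |

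Example, w = 0.3, case A: 0.348 × 0.98875² = 0.340.

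**The case against.** The strongest counter-argument is that the deciding document was not available. Protocol 11 sends assessment detail to the Manual of Procedures, and Protocol 14.4 refers to training and detailed instructions there. A rule on starting point or test order would naturally sit in it. This stands as a limit: the finding concerns the protocol and SAP only. But SAP 1.4 closes off any further masking, so a mask in the Manual would contradict it and would still need to be cited.

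The contrast between the numbered lists and the Section 5 table is weak evidence, because that table is a grid of assessments by visit and not a sequence. This is accepted. The three lists agree on device first, and a site following them would have the KR-1W reading in hand before manifest refraction.

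The magnitude is hypothetical. The pull has no source in the documents. The SD comes from first-eye versus second-eye differences, not from manifest versus device readings. At a true difference of 0 a pull causes no bias in the mean. Part of the 34% arises because the two truly equivalent sites pass more often; holding them at 80.0% gives 0.348 × 0.800² = 22%. All of this stands, and the figures are a sensitivity range only.

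Finally, if sites normally start from an objective reading, barring the KR-1W changes the manifest refraction being compared. The documents do not say what usual practice is. This is a real trade-off, and the sponsor should settle it openly.

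**Conclusion.** The concern holds and should be fixed, with medium confidence. Following the protocol and SAP as written, the examiner may see and use the comparator's result before producing the subjective measurement, and any resulting error favours the study's conclusion. The documents show that this is possible, not that it will happen.

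For a pull of 10% to 30%, per-site false equivalence at a true difference of 0.15 goes from 5% to between 9% and 35%. The per-site risk matters because the objective is stated for each site. At study level the every-site rule keeps the risk below 5% throughout this range if all three sites sit at the margin. With one site at the margin and two at zero, it rises from 3.2% to 14% (mean only) or 34% (mean and SD) at a 30% pull. These results rest on an assumed pull, independent sites and the planning SD.

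**What to change.** - **Protocol 10.4 and SAP 1.4:** add that the examiner performing postoperative manifest refraction is masked to that visit's KR-1W refraction and does not use any KR-1W refraction as a starting point. Amend the closing sentence of SAP 1.4 to match.
- **Protocol 11.3 and 11.4:** state that manifest refraction is completed and recorded before KR-1W capture, and re-order those steps. Visit 2 supplies the primary endpoint; Visit 1 is included so that practice is the same at both.
- **Protocol Section 5:** add a footnote giving the order.
- **Earlier readings:** where existing staff and records allow, do not give the examiner KR-1W values from previous visits. Re-ordering alone does not hide these.
- **Manual of Procedures:** align it. If it already contains these controls, cite it in Protocol 10.4 and SAP 1.4.

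The cost is wording. The current-visit mask needs no extra examiner when manifest refraction comes first, and the sample size and analysis do not change. The examiner loses a time-saving starting point and the visit order becomes fixed.
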